5.1.3 Study Visit 3- data prompted interview (week 4-12)

Semi-structured data-prompted interviews will be used to explore participant experiences and perceptions of diet, physical activity behaviours, and weight management. Using personalised data as a prompt during the interview, can aid an individual's recall of events and decision making and be a more accurate method of retrospective qualitative data collection (73). Semi structured interviews are a qualitative research method that gathers data on personal experiences and views on an issue. An interview structure of open-ended questions, with follow up questions and probes are used to facilitate more in-depth exploration.

Semi-structured data prompted interviews will be conducted with 20 - 30 participants. Interview participants will be selected to maximise variation and has been suggested as sufficient when there is a specific research question(74). Following initial analysis of 20 interviews, if new issues emerge after these interviews, further sampling will be employed for additional participants to take part in data prompted interviews to reach data saturation

Interview Procedure

A mutually convenient date, time and preferred location for interview will be arranged with them; in a private clinic room at WMACFC/SACFC/NWMCFC/WCFC, in the participant's home or by video using a University of Birmingham Zoom© or Microsoft Teams© video conferencing platform account.

If Visit 3 takes place at the participants home, the CI will adhere to University of Birmingham Guidance on Out of Hours Activities and Lone Working. The visit will be risk assessed.

JB will verify ongoing agreement to participate and the participant will have the opportunity to ask any questions. The interview will commence and audio recording will be started using an encrypted voice recorder. If the interview is being conducted by video using the Zoom© video conferencing platform, the interview will only be audio recorded using the platform recording function and the platform transcription facility will be used to record speech to text. If the interview is being conducted by video using Microsoft Teams© video conferencing platform, the interview will be audio and video recorded using the platform recording function and the platform transcription facility will be used to record speech to text A visual summary of the participants food and physical activity data will be used as a prompt with a series of open questions, framed around the study objectives to stimulate the participant to talk about their experiences, perceptions, views, and opinions (see appendix for interview schedule). Probes and follow up questions will be used to explore the topics/views and elicit more detail from the participant. Interviews are estimated to take up to approximately 60 minutes. At the end of the interview the CI will summarise to verify what has been said and thank the participant for attending.

The audio file will be uploaded to Microsoft Word 365 and transcribed using the automated transcription function by [name]. Microsoft Word 365 will be accessed through the University of Birmingham secure server. The transcription will be saved on a University of Birmingham server as soon as possible not exceeding 4 weeks and then deleted from the encrypted voice recorder. Transcriptions from the audio recordings will be downloaded from the University of Birmingham Zoom© or Microsoft Teams© video conferencing platform account and saved on a University of Birmingham server as soon as possible not exceeding 4 weeks and then deleted from the platform.

Following initial analysis of the first 20 interviews, the quality of data and depth of themes generated (saturation) will determine if more participant interviews are required.

Interview Questions

The interview guide has been developed from the COM-B model, knowledge gaps identified in the literature, and the background and experience of the research team; Specialist CF Dietitian [name] – Chief Investigator (CI), qualitative research expert and nurse ([name]), and Associate Professor of lifestyle behaviour change ([name]) and the MLCFPAG. It aims to stimulate a narrative and exploration of the participant's experience and perceptions of their diet and physical activity behaviours, influences on

these behaviours, and their experience of weight management since CFTR modulator therapy (see appendix for interview schedule).

The interview schedule was revised in response to feedback from the MoreLife with CF Patient Advisory Group and Lead Partners.

Post Interview

At the end of the interview, the Microsoft Word transcription and voice recording will be saved on a password protected server at the University of Birmingham (Data Management Plan) and deleted from the encrypted voice recorder.

CI will record field notes of personal assumptions, responses, and thoughts in a reflexive diary. Any minor amendments to structure, ordering of topics, or rephrasing of questions that may be required to enhance clarity will be identified and discussed with AT and SF. In line with the inductive approach, interview questions will then be modified if necessary to include emergent issues may be required for the next interview.

5.1.4 Data Analysis

The quantitative and qualitative data will be analysed separately and integrated;

Descriptive statistics will be performed on all quantitative outcomes using SPSS vs 27 (75)

Quantitative Data Analysis

The self-reported food intake diary will be analysed using myfood24® nutritional analysis software(76). The food diary and nutrient intake data will be generated from MyFood24® (see appendix) in a Comma Separated Values (CVS) output file and saved on a University of Birmingham password protected server (see Data Management Plan (DMP)). Participants who complete less than 3 days food records will be excluded from the dietary data analysis, as it is unlikely to be a true representation of their habitual food intake and will not be approached for interview

Daily mean nutrient intakes will be calculated for each participant, across the number of days completed food diary data. For macronutrients and free sugars, both total and total food energy-adjusted values (per 1000kcal) will be reported employing Atwater factors(77). Fibre will be quantified using the Association of Official Analytical Chemists (AOAC) method. Nutrient intake data will be compared to Dietary Reference Values for food and Nutrients in the UK(78), Scientific Advisory Committee on Nutrition Recommendations(79-81), European Cystic Fibrosis Nutrition Guidelines(82);

In addition, percentage distribution of nutrients (energy, fat, carbohydrate, total sugar, protein, fibre, calcium) per meal (breakfast, lunch, evening dinner, snacks, drinks) will be summarised and the top 5 foods that contribute to intake of energy, fat, carbohydrate, total sugar, protein, fibre, and calcium will be tabulated.

Physical Activity Data

Participants accelerometery data will be downloaded, analysed and stored using Actilife® software (version 6.2)(72). This software will be accessed via and the data will be stored on a University of Birmingham password protected computer server. Once the data has been downloaded the participant data will be cleared from the device. The physical activity data will be summarised and exported as a pdf file and saved on a University Hospitals Birmingham password protected computer server A summary of this data will be entered into the participant Case Report Form. Non-wear time will be determined by Actilife® software. Participants with < 10 hours valid wear time per day, for <4 days, will be excluded from the analysis. The amount of valid wear time will be used as a co-variate in any statistical analysis, to account for variability between participants.

Accelerometer cut-points will be used to compute average total daily sedentary time (SED), light-intensity physical activity (LPA), and moderate-to-vigorous-intensity physical activity (MVPA) (83-86).

Qualitative Data Analysis

The audio-recording and transcription will be imported into NVivo 12(87). NVivo 12 will be used to organise, and chart the focus group interview data.

The framework approach will be used to analyse the data (52, 88). This method has been chosen as it is a systematic process for organising, reducing, and interpreting qualitative data. It guides a process of thematic analysis with the development of an analytic framework and charting matrix from the coding and categorising of interview data to aid the comparison across the data set so that relationships, and patterns can be developed into key themes. An advantage of this method is the inclusion of participant accounts in the matrix ensure that individual descriptions and interpretations are not lost in the analysis.

The following process of the framework approach will be used to analyse the data;

i. Transcription

Following each interview, JB will check the transcription for errors by listening back to the audio-recording and reading the transcripts simultaneously. Corrections will be made to ensure an accurate verbatim transcription for analysis.

ii. Familiarisation with the interview

JB will listen back/view to the audio recording and read and re-read the transcript to familiarise with the data thoroughly. Initial analytical thoughts on the key study objectives, relevant issues that emerge and impressions will be noted.

iii. Independent Coding

JB will independently code data from the first 5 interviews. The transcription will be read line by line and coded by applying a descriptive label to a section of text that is significant or relevant to summarise and described what has been said by each participant.

iv. Develop analytical framework and then discuss to form a consensus of a set of codes to apply to future transcripts

JB will discuss their independent coding with AT and agree on a set of codes. Codes that are conceptually related will be grouped together into clearly defined categories. This coding index will form the analytical framework which JB will then be applied to subsequent transcripts.

v. Applying the analytical framework

The analytical framework will be used to code and categorise subsequent interview transcripts. Any new codes which emerge from the subsequent interviews will be discussed by JB with AT to reach a consensus and the framework will be updated to incorporate new codes.

vi. Charting the data into the framework

Once all the data has been organised into categories and codes using the analytical framework, a matrix will be constructed; one spreadsheet for each category and a column for each code within that category. Codes from each transcript will be summarised and charted into the Matrix. Illustrative participant quotations will also be charted into the matrix. JB will chart the data and this will be reviewed by AT. Any differences of opinion will be discussed and the charting will be revised considering agreed changes.

vii. Interpreting the data

Influenced by the key study objectives, JB will interpret he data by using the matrix to compare across categories and codes, between and within individual participant data to identify any connections or patterns. Codes and categories will be mapped to the COM-B framework and developed into themes and subthemes. Themes and subthemes will be further developed in discussion with AT.

viii. Validation of Themes and Subthemes

The MLCFPAG and study steering group committee will be provided with the opportunity to review the pseudonymised research findings(89). This feedback will be discussed with AT and the themes and subthemes will be refined in response to feedback received.

Quantitative and Qualitative Data Integration

The quantitative (descriptive statistical summary of nutrient, food intake, and physical activity data) and qualitative results (themes and subthemes) will be integrated using joint display analysis (90, 91). The data sets will be illustrated together to enable them to be compared and explored to identify and understand contextual factors that influence diet and physical activity behaviours, how perceptions compare to quantitative data. Relevant health behaviour theories will be examined to explain the psychological mechanism of action of the behaviours and a preliminary logic model will be constructed.

The results will be used to formulate guiding principles for CF weight management programme.

6. Project setting

This study will recruit participants from 4 sites; West Midlands Adult CF Centre, University Hospitals Birmingham, Heartlands Hospital (WMACFC) and Sheffield Adult CF Centre, Northern General Hospital, Sheffield (SACFC), North West Midlands Cystic Fibrosis Centre, Royal Stoke University Hospital NHS Trust (NWMCFC) and Wolfson Cystic Fibrosis Centre, Nottingham University Hospital NHS Trust (WCFC)

Study visits will take place at the WMACFC/SACFC/NWMCFC/WCFC, the participants home or virtually via a video-conferencing platform using a University of Birmingham Zoom© or MS Teams© accessed via the university's secure server.

7. Participant recruitment

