- IV. the purpose of the research and the importance of recording their 'usual' food intake will be explained to the participants to minimise reporting bias. Participants will be advised that they will not be judged on their diet, and they should avoid making dietary changes during the recording period.
- V. participants will also be able to contact the CI for additional app support by phone or email.
- VI. A date will be agreed with the participant when they will commence recording their food intake. Participants will receive a reminder notification from MyFood24 to complete a food diary for each day. Participants completing a paper diary will receive a text message reminder from CI during the monitoring period in week 1 and 2. MyFood24 dietary target notifications will be turned off to minimise this influencing their food intake e.g., modifying it in response. The participant will be provided with information on how to use the app and links to 'YouTube' videos in their study information booklet (see appendix).
- VII. At the end of their participation in the study the participants will be advised to delete the MyFood24 app.

Physical Activity Monitoring

Accelerometery will be used to measure physical activity over 14 days. Physical activity is defined as any bodily movement produced by skeletal muscles resulting in energy expenditure (67). Sedentary behaviour is defined as sitting, reclining, or lying postures, excluding sleep, with energy expenditure of ≤1.5 metabolic equivalents (METs)(68). Accelerometers are electronic devices capable of continuously recording changes (accelerations) in

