movement. Triaxial accelerometers measure movement in three axes (directions); X (left to right), Y (forward and backward), and Z (up and down). Data can be analysed to provide an estimate of time spent in different frequencies, intensities, and durations of physical activity. Seven days wear (≥10 waking hours/day) is usually considered a sufficient time to gather data on habitual physical activity patterns (69). Longer wear periods are recommended where adult populations may demonstrate higher variability in levels of physical activity week to week (70). In this study, the measurement time frame will therefore be 14 days of continuous wear (including overnight), to ensure habitual levels of physical activity are reliably captured. Overnight wear also helps to increase compliance, and provides important data on sleep (quantity, efficiency), which is important to understand when investigating physical activity (69).

Participants will be provided with an ActiGraph wGT3X-BT monitor (Actigraph, Pensacola, Florida, USA), either in person at visit 1 or by post from the Chief Investigator following this visit. They will be instructed to wear this on their non dominant wrist for 14 days. The participant will be advised to wear the monitor for at least 10 hours a day up to 24 hours per day. They will be advised that the monitor is not waterproof and they should not wear it whilst swimming, taking a bath or a shower. A date, time and location for study visit 2 will be arranged with the participant (2 weeks' time from study visit 1). The participants GP will be informed of their participation in the study by letter.

5.1.2 Study Visit 2- Verification of Food Diary and Return of Physical Activity Monitor (week 3-7)

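### The accelerometer rules never say that worn sleep is removed, so sedentary time and the valid day as written do not match the protocol's own waking-hours definitions

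*Protocol*

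**What the plan says.** Section 5.1.1 of the protocol, under Physical Activity Monitoring, sets the concepts and the wear schedule:

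- Definition: "Sedentary behaviour is defined as sitting, reclining, or lying postures, excluding sleep".
- Cited wear standard: "Seven days wear (≥10 waking hours/day) is usually considered a sufficient time".
- Schedule: "the measurement time frame will therefore be 14 days of continuous wear (including overnight"). One reason given for night wear is that it "provides important data on sleep (quantity, efficiency").
- Instruction to participants: "The participant will be advised to wear the monitor for at least 10 hours a day up to 24 hours per day".

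Section 5.1.4, under Physical Activity Data, sets the processing. The software determines non-wear. Participants are excluded by a rule based on 10 hours of valid wear a day and 4 days; the word waking does not appear in it. Then: "Accelerometer cut-points will be used to compute average total daily sedentary time (SED"), together with light and moderate-to-vigorous activity. On differences in wear: "The amount of valid wear time will be used as a co-variate in any statistical analysis". The opening of the same section says: "Descriptive statistics will be performed on all quantitative outcomes".

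**The concern.** The definition and the cited standard both refer to waking time, while the processing rule refers to wear. With night wear planned, the two are not the same. A sleeping person wearing the device moves little, so unless sleep is identified first, the night can pass the wear filter, help to fill the 10 hours and fall into the lowest intensity band.

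The error would not be a constant that cancels between people. Participants may wear the device for anything from 10 to 24 hours, so some records will hold nights and others will not. Reported sedentary time would then partly reflect night compliance.

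Objective ii is to characterise activity patterns and level by accelerometry. Each participant's summary is also shown back as the prompt at the visit 3 interview, and the group results enter the joint display and the guiding principles. Group summaries can be reprocessed from stored data. An interview already held around an inflated figure cannot be repeated in the same way.

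**Working it through.** The plan gives no figure to reproduce: this is a processing rule, and no sample size or error rate depends on it. The check has two parts.

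**1. Texts side by side**

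| Item | Section 5.1.1 | Section 5.1.4 |
|---|---|---|
| Sedentary time | sleep excluded | cut-points applied; time window not stated |
| Wear standard | 10 or more waking hours | 10 hours of valid wear |
| Night data | collected, partly to measure sleep | no sleep step; non-wear is the only removal named |

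No sleep detection, sleep log or waking window is described anywhere in the protocol.

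**2. Possible size**

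Inputs from the protocol: the 10-hour rule and wear of 10 to 24 hours a day. Assumptions, because the protocol gives neither: sleep s of 6 to 9 hours, and true waking sedentary time of 9 hours a day (8 to 10 as a range).

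- Waking wear needed to pass the 10-hour rule, if all sleep is worn and counted = 10 − s.
- Reported sedentary time with full night wear, all sleep scored sedentary = 9 + s.
- Mean excess if half the nights are worn = 0.5 × s.

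| Sleep worn (h) | Waking wear needed (h) | Reported sedentary time (h) | Ratio to 9 h | Mean excess, half the nights (h) |
|---|---|---|---|---|
| 6 | 4 | 15 | 1.67 | 3.0 |
| 7 | 3 | 16 | 1.78 | 3.5 |
| 8 | 2 | 17 | 1.89 | 4.0 |
| 9 | 1 | 18 | 2.00 | 4.5 |

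With waking sedentary time of 8 to 10 hours, full night wear gives 8 + 6 = 14 to 10 + 9 = 19 hours. The same person taking the device off at night reads 8 to 10.

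These are upper bounds. If the software flags still sleep as non-wear, the excess shrinks, to zero if all of it is flagged. No non-wear algorithm is named, so the protocol supports only the range from 0 to s.

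**Does adjusting for total wear repair it?** Take 8 hours of sleep and 9 hours of waking sedentary time. With the device off at night, the share of wear is 9/16 = 56%. With the device on all night it is 17/24 = 71%. Behaviour is identical, yet the shares differ, because total wear mixes sleep with waking time.

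**Light and moderate-to-vigorous activity.** Sleep adds no minutes to moderate-to-vigorous activity. The risk is indirect: a day with few waking hours worn would pass as valid and understate both measures on that day.

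**The case against.** The strongest reply is that the protocol should be read as a whole. Sedentary behaviour is defined once, without sleep, and that definition governs the term wherever it appears. Sleep quantity and efficiency cannot be obtained without finding the sleep periods, so detection is implied. The algorithm and the order of steps are details that an analysis plan commonly supplies.

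Much of this stands, and it rules out several stronger readings that a reader might infer:

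- That the protocol directs sleep to be counted. No sentence says so, and the definition says the opposite.
- That 8 hours (480 minutes) a day is the expected bias. It is an upper bound that needs 8 hours of sleep, all of it worn, none flagged as non-wear and all scored sedentary.
- That valid days made mostly of sleep will be common. They need someone who wears the device all night and removes it for most of the day, and nothing in the protocol suggests that this is frequent.
- That the wear-time covariate is a failed remedy for sleep. It is offered to allow for differences between participants, and only for whatever statistical analysis is done. The protocol specifies no model, and the planned summaries are descriptive, so the sentence may have nothing to act on; that does not make it wrong.

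The reply does not dispose of the point. The choice of sleep algorithm can be left to an analysis plan, but Section 5.1.4 does fix a validity rule, and that rule drops the waking condition that Section 5.1.1 cites. It also sets out a sequence of processing in which non-wear is the one exclusion named. An analyst who follows it literally does not obtain the quantity defined.

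**Conclusion.** The point holds as a mismatch between the stated processing and the protocol's own definition and cited standard. Followed as written, worn sleep can count towards a valid day and into sedentary time. The excess is between 0 and the full sleep time worn: at most about 6 to 9 hours a day under assumed sleep of 6 to 9 hours, and unequal between those who do and do not wear the device at night. Its actual size depends on night compliance and on the unnamed non-wear algorithm, neither of which the protocol settles.

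The consequences are limited by the design. Priority is given to the qualitative data, and none of the outcomes listed in Section 4.2 is itself an activity estimate. What is exposed is objective ii and, less reversibly, the individual summaries used at interview. That makes correction worthwhile before further summaries are produced.

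**What to change.** In Section 5.1.4, Physical Activity Data:

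1. State that sleep periods are identified and removed before the valid-day and cut-point steps.
2. Define a valid day as one with at least 10 hours of waking wear.
3. Compute sedentary, light and moderate-to-vigorous time on waking wear only, and report each in minutes and as a percentage of waking wear time.
4. Report sleep separately.
5. Apply these steps before each participant's interview summary is made.

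The covariate sentence may stay for any model that is fitted, provided that the covariate is waking wear time.

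The cost is a change of wording and one extra processing step on data already being recorded, with no added burden on participants. Some days dominated by sleep will become invalid, and a participant with few valid days could fall below the 4-day minimum.

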Study visit 2 will take place in a mutually convenient time; face to face in a private clinic room at WMACFC, SACFC, NWMCFC, WCFC or in the participants home, alternatively remotely by phone or via a videoconferencing platform using a MS Teams/Zoom© University of Birmingham account via the University of Birmingham secure server. If via videoconferencing participants will be sent an invitation link to the virtual meeting room by email. The link will have a passcode which will only be available to the participant. The option of interviewing via video has been included to facilitate interviews with participants located a considerable distance from their CF centre and throughout the UK. Video interviews will also give more flexibility for interview date and time for those participants who are not available during normal working hours.

If Visit 2 takes place at the participants home, the CI will adhere to University of Birmingham Health and Safety Guidance on Home Visits . The visit will be risk assessed.

i. Food diary Verification

JB will view participants food diary data via the MyFood24 web-based platform and check with the participant that that the correct food type has been entered, portion sizes are accurate and probe if any food items have not been recorded using a checklist (see appendix) and pictorial portion size food Atlas(71). Incorrect or absent entries will be amended by CI in agreement with the participant.

ii. Physical Activity Monitor

The physical activity monitor will be returned by the participant. If study visit 2 takes place virtually, they will be asked to either; 1) return the physical activity monitor by post in a pre-paid envelope to the CI/PI at WMACFC/SACFC/NWMCFC/WCFC, 2) JB will arrange to collect from the participants home, or 3) a member of the CF Team will arrange to collect the monitor from the participants home during a scheduled clinical home visit (adhering to university home visit or local lone worker policies). Once the physical activity monitor has been returned by the participant, they will be sent a £10 retail voucher. All participants who take part in the study will be invited to join the co-design team for the next phase of the study by letter which will be sent with the retail voucher.

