The participants physical activity data recorded on the ActiGraph wGT3X-BT (Actigraph, Pensacola, Florida), USA) will be downloaded via the Actilife software (using Actilife® software (version 6.2)(72) on a University Hospitals Birmingham password protected computer as soon as possible once the device being returned, not exceeding 2 weeks after being received by the Chief Investigator. Once the data has been downloaded the participant data will be deleted from the device. The device will then be cleaned using disinfectant wipes. Data is linked by participant ID only.

Each participants food diary, eating pattern and physical activity data will be summarised in a visual format to use as a data prompt to stimulate discussion during the semi-structured interviews. A copy of the food diary and physical activity summaries will be entered in the paper and electronic CRF. These will be saved on a University of Birmingham password protected server (see Data Management Plan)

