10.4. Patient & public involvement

The MoreLife with CF Patient Advisory Group was established for this research (MLCFPAG) and there are Lead Partners for this research; [name] and [name]. A series of online meetings were conducted by the Chief Investigator (JB) with the MLCFPAG to gather feedback on the study design and methods, interview schedule, trial of food diary app and all patient facing documents. Open feedback and questions were invited at the sessions and the group was also able to provide feedback using an anonymous online Jamboard®. Additionally, online anonymous surveys were conducted to gather feedback from the WMACFC population. The key points from feedback were as follows;

- 4 days food diary records and 14 days physical activity monitoring was acceptable
- The MyFood24 food diary smart phone app has been chosen for participants to record food intake as it was preferred to an alternative app.
- The terminology that is acceptable to be used in the protocol should be 'overweight'
- The terminology that should be used in participant information and study adverts should be unwanted weight gain (most popular) followed by high BMI, gene modulator weight, excess weight
- Participants should be sign posted to social work if financial difficulties become apparent during interviews
- The interview schedule had the following amendments in response to feedback to start with exploring experience of CFTR modulator therapy and weight and to include questions about diet and physical activity when people are well/unwell.
- The Participant Information Sheet had the following amendments; to include an explanation on why
 participants would be asked to about household income and educational status and to change the
 order of point 9 and 10, to include a short explanation of what the study is about at the start of the
 PIS.
- An incentive should be offered to participants for taking part in the research a £10 Amazon voucher

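### Perceptions to be compared with the diet and activity data come only from an interview prompted by those data, and the protocol states no unprompted question beforehand

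*Protocol*

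**What the plan says.** Four parts of the Protocol bear on this.

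- **Building the prompt (section 5.1.2, Study Visit 2).** Each participant's food diary, eating pattern and activity data are "summarised in a visual format to use as a data prompt to stimulate discussion during the semi-structured interviews". At the same visit the diary is checked with the participant: "Incorrect or absent entries will be amended by CI in agreement with the participant".
- **Eliciting perceptions (section 5.1.3).** "Semi-structured data-prompted interviews will be used to explore participant experiences and perceptions of diet, physical activity behaviours, and weight management". In the interview procedure, "A visual summary of the participants food and physical activity data will be used as a prompt with a series of open questions". The stated reason for prompting is that it helps recall of events and decisions and can "be a more accurate method of retrospective qualitative data collection".
- **Order of the interview (section 10.4).** After patient feedback the schedule was changed "to start with exploring experience of CFTR modulator therapy and weight", and questions on diet and activity when well and when unwell were added. The schedule itself is an appendix that is not in the available text.
- **Integration (section 5.1.4).** The interview themes are placed in a joint display beside the "descriptive statistical summary of nutrient, food intake, and physical activity data". One stated purpose is to see "how perceptions compare to quantitative data".

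**The concern.** A comparison of what people perceive with what was recorded is informative only if the perception was formed without sight of the record. Here the record is the stimulus for the interview that supplies the perception. An answer given with the summary in view may be a reaction to it rather than the belief the participant brought to the interview.

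The stake is limited but real. Perceptions of diet and activity are an objective of the study (section 4.1, iii). The integrated results feed the logic model and the Guiding Principles for the weight management programme. A gap between belief and behaviour is relevant to the COM-B mapping, for example to psychological capability and motivation. If the display mutes that gap, the joint display would understate it.

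**Working it through.** The protocol gives no figure for this comparison, so there is none to reproduce. The check traces how the data flow and when.

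1. **Measurement, from visit 1.** A 4-day food diary and 14 days of accelerometer wear (section 5.1.1).
2. **Review, visit 2.** The diary is gone through and amended with the participant. The monitor is returned, and its data are downloaded after return (section 5.1.2). No showing of activity results to the participant is described at this visit.
3. **Display, visit 3.** The visual summary built from steps 1 and 2 is the interview prompt, for 20 to 30 participants (section 5.1.3). This is the first stated point at which participants see their activity data.
4. **Comparison.** Themes from visit 3 are set beside a descriptive summary of the step 1 measurements (section 5.1.4).

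The two sides of step 4 are therefore linked through step 3. They are the same measurements at different levels of aggregation: individual in the prompt, a descriptive summary in the joint display.

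**Is a safeguard stated?**

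- Section 5.1.3 describes no unprompted question on the participant's own diet or activity level.
- The only stated ordering (section 10.4) opens with modulator therapy and weight, which is not a self-assessment of diet or activity. Where the well/unwell questions fall relative to the summary is not stated.
- The framework steps in section 5.1.4 do not separate statements made before and after the display.
- The integration paragraph carries no caveat.

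By contrast, section 5.1.1 turns off dietary target notifications in the app so that they do not influence intake. The protocol thus recognises that feedback can alter what is being observed.

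**Direction.** Suppose a voiced perception is a mixture of the prior belief and the displayed value, with weight w on the display:

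voiced = (1 − w) × prior + w × displayed

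Subtracting the displayed value gives:

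voiced − displayed = (1 − w) × (prior − displayed)

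For any w between 0 and 1 the visible gap is smaller than the true one. At w = 0 it is unchanged, and at w = 1 it vanishes. The documents give no value for w, so this fixes the expected direction and not the size.

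**Diet and activity differ.** The diet data are self-reported, recorded by the participant and then agreed at visit 2. A diet perception given at visit 3 is already informed by them, even before any summary appears. Nothing comparable is described for the accelerometer data, so an unprompted perception of activity can still be obtained at visit 3.

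**The case against.** The strongest reply has four parts.

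- **The order of questions belongs to the interview schedule, which was not seen.** This stands. It cannot be said that no unprompted question exists, only that the protocol body states none. Even if the schedule has one, section 5.1.4 does not say which statements enter the comparison.
- **Prompting is a deliberate and legitimate method with a stated reason.** This also stands. For recall, context, decisions and barriers the prompt is well chosen and should stay. But a tool chosen to bring accounts closer to recorded events is poorly suited to showing how far perceptions depart from them.
- **The accuracy of self-judgement is not among the objectives or outcomes, and the comparison is one clause.** This limits the importance of the point. The clause is nevertheless a stated purpose of the joint display, and it should be answerable by the method used.
- **A participant shown the data can express surprise or dispute them, which reveals a gap.** True. Disagreement is made less likely, not excluded.

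A reader might infer more than the documents support. They do not say that the summary is shown at the outset, only that it accompanies open questions. They do not specify which activity or nutrient measures it contains. They plan no numerical self-rating and no correlation, so no inflation of a coefficient can be claimed. Nor do they plan a conclusion that participants judge their own diet and activity accurately.

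**Conclusion.** The point holds in a limited form. As the protocol body is written, the perception side of this one comparison is not independent of the data side, and the expected tendency is towards agreement. The size cannot be estimated from the documents. All 20 to 30 interviews use the prompt, but how far any answer is altered is unknown.

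The conclusion rests on two assumptions: that the schedule does not already ask for unprompted perceptions of diet and activity, and that the displayed data carry some weight in what participants then say. If the first is wrong, what remains is to specify which statements are compared.

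The rest of the qualitative work, including the exploration of experiences, barriers and facilitators, is not put in question. The change is worth making because it costs little, and because an unprompted answer cannot be recovered once the data have been shown.

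**What to change.** - **Section 5.1.3, Interview Procedure.** State that each interview asks, before the visual summary is shown, how active and how sedentary participants think they are and how they would describe their usual diet. The summary is then revealed and the data-prompted questions follow as planned. If the schedule already does this, say so here.
- **Section 5.1.4, framework analysis and integration.** Base the comparison of perceptions with data on the pre-reveal statements. Code post-reveal statements separately as reactions to the data; these remain useful for the other themes.
- **Caveat for diet.** State in the integration paragraph that diet perceptions are already informed by self-recording and by the visit 2 review, so that part of the comparison is weaker than the part for activity.
- **Interviews already held.** Where no pre-reveal answer was taken, keep the interview in the thematic analysis but mark it as not contributing to this comparison.

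The cost is a few minutes per interview, one extra code and a short addition to each of the two sections. Section 5.1.3 already allows minor changes to topic order after discussion with the supervisors. The prompted method and the sample are unchanged. If reordering is not wanted, the alternative is to drop the comparison clause or qualify it throughout.
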